#### **After baseline evaluation:**

##### *Polysomnography (PSG)*

All patients, both intervention and waiting list group, will administer three nights of self-applied PSG (hereinafter called SAS). This is an alternative to in-lab services and PSG setups, in a self-applied form. The EEG is located only on the forehead (F-channels), with no electrodes located on the top of the scalp (C-channels) and back of the head (O-channels) as in traditional PSG. The self-applied setup facilitates

the use of multi-night studies to capture night-to-night variability and the participants apply the sensors themselves, using an instructional video provided by Nox. In this study, we will do three nights in a row twice. PSG will be performed before the baseline consultation and before the outcome evaluation. The equipment will be given out at baseline consultation. After use the patients will mail the equipment back to Ahus/FPH or bring the equipment back to the first treatment session.

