### ***3.2 Methods***

#### **Prior to the baseline consultation**

All participants will receive a standardized information sheet with login information to the electronic sleep diary. Support on using the application prior to the baseline evaluation will be available by the study co-ordinators by telephone. Evaluation of exclusion criteria will be assessed prior to- or at the baseline study visit. Excluded patients will be referred back to clinical care. Signed informed consent will be obtained and archived on paper.

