### **Baseline evaluation**

Eligible candidates completing auto-monitoring less than 70% of the days prior to baseline assessment will be excluded (see exclusion criteria above). Questions related to the “Sleep Well” application will be answered. [name] and [name] respectively will also ensure that at least 40 of 100 participants are female. After final inclusion, [name] and [name] respectively will schedule the sleep registration and an outcome evaluation session 90 days later. All data collected during the baseline evaluation will be collected in the “Redcap” case report form (CRF).

Further, clinical evaluation will consist of height, weight, standardized blood pressure and a breath holding test. Digital oral scanning will be obtained at both sites. Thereafter, the quantitative scores (OMES) for assessing the myofunctional therapy will be performed and video filmed with one front camera and one camera with a 45-degree angle on the face. The purpose of the video filming is inter rater reliability analyses. All participants will be placed in a chair without arm- or backrest. Body posture on the chair will not be corrected. The baseline assessment will last approximately 90 minutes.

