#### **Randomization**

At the end of the baseline consultation participants will be randomized to either OMTa or only auto-monitoring. Block-randomization with 10 lots per block, per study site, and a 50/50 allocation ratio will be used for waiting list and intervention and separated by sex in order to monitor the 40/60 gender balance. The lots will be made as a code on paper and concealed in opaque envelopes at each study centre. Each participant will also receive a unique e-mail address and a password in the same envelope. The randomization envelopes will be made and mixed by dr. [name]. Envelopes will be sent to dr [name] in Estonia. Both researchers will be blinded for the content in the envelopes.

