### **Description of the intervention**

Participants opening a code unlocking the OMTa treatment module of the application will be given a direct communication link to the PhD students, [name] (Norway) and [name] (Estonia) and two research co-ordinators. [name] and [name] has obtained an Academy of Orofacial Myofunctional Therapy (AOMT) certification diploma. One physical start up session will be scheduled at Ahus and at North Estonia Medical Center. This 60 minute session will be used to instruct participants in OMT exercises and use of the app. All participants will receive a disposable toothbrush and standardized balloons. After that, biweekly video sessions (time 20-30 min) will be scheduled. The exact same amount of sessions and equipment will be offered to the waiting list group after the outcome evaluation. The following exercises are pre-recorded and presented in the treatment module:

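### The protocol contradicts itself on whether the first three-night PSG series, the inferred source of baseline AHI, is recorded before or after the visit that ends with randomisation

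*Combined protocol and SAP*

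**What the plan says.** All references are to the combined protocol and SAP.

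- *Polysomnography (PSG)*, placed under the heading *After baseline evaluation*, plans two series of three consecutive self-applied nights: "PSG will be performed before the baseline consultation and before the outcome evaluation. The equipment will be given out at baseline consultation". Participants then mail the equipment back or "bring the equipment back to the first treatment session".
- *Randomization*: "At the end of the baseline consultation participants will be randomized to either OMTa or only auto-monitoring".
- *Prior to the baseline consultation* lists what happens before the visit. It includes "All participants will receive a standardized information sheet with login information to the electronic sleep diary", telephone support, the exclusion check and "Signed informed consent will be obtained and archived on paper". It mentions no PSG kit.
- *Baseline evaluation*: after final inclusion, staff "will schedule the sleep registration and an outcome evaluation session 90 days later".
- *Description of the intervention*: the start-up session teaches the exercises to the OMTa arm. For the controls, "The exact same amount of sessions and equipment will be offered to the waiting list group after the outcome evaluation".
- *Outcomes*: the primary endpoint is change in AHI, with no recording or time window named for the baseline value.

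**The concern.** A baseline for a change endpoint should be fixed before allocation can influence it. If the first series follows randomisation, participants in an open-label trial apply their own sensors at home at a time when they may know their arm. Someone assigned to the waiting list may be less inclined to complete three nights or to apply the sensors carefully, or the reverse may hold. Missing baselines and recording quality could then differ by arm. Scoring by technologists at a separate institute does not repair nights that were not recorded, or were recorded differently.

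There is also a practical problem. Two sites could each follow a different sentence and both be following the protocol, so the baseline could mean different things in Norway and Estonia.

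**Working it through.** The point concerns the order of events, so the check is a comparison of sections.

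**Step 1: the two sentences.** The first puts series one before the baseline consultation. The second issues the equipment at that consultation. Both cannot hold for series one. Because randomisation closes the same visit, the first sentence gives a baseline before randomisation and the second gives one after it.

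**Step 2: evidence on which reading is meant.**

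| Evidence | Points to |
|---|---|
| First sentence of the quoted pair | before the visit |
| Hand-out sentence | after the visit |
| Section heading (*After baseline evaluation*) | after the visit |
| Pre-visit list without a PSG kit | after the visit |
| Sleep registration scheduled after final inclusion | after the visit, though the wording could mean the second series |
| Kit returned at the first treatment session | after the visit, and before supervised exercises |

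Recording after the visit is the better-supported reading, but it is not settled.

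**Step 3: can the sentences be reconciled?** The hand-out might concern only the second series. That does not fit the return point: in the OMTa arm the first treatment session is the start-up session, which precedes any outcome recording. Nor is an earlier hand-out for the first series described anywhere.

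**Step 4: link to the primary endpoint.** The link is an inference. The *Outcomes* section gives no source for AHI, but it names the self-applied recording for other OSA parameters, and no other repeated sleep recording is described.

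**Step 5: what is reached.** Section 6.1 does not define T1 and T2. Taking them as baseline and outcome, the order matters for change in AHI, for the T1 comparison and for the within-group tests. The T2 between-group comparison uses no baseline and is untouched. The recordings in question are the whole first series: 100 planned participants × 3 nights = 300 nights. That is the extent of the ambiguity, not a measure of bias.

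**Step 6: the plan's own figure.** Section 6.2 gives 26 per group for d = 0.8, two-sided 5%, power of at least 80%. The normal approximation is 2 × (1.960 + 0.842)² / 0.8² = 24.5, so 25. The t-test solution is 25.52, so 26, with power 80.7%. The figure reproduces, and neither reading of the PSG timing changes it.

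**The case against.** The strongest case for the plan accepts the conflict but disputes its consequence.

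- **Participants may not know their arm during these nights.** This stands. Section 3.0 ties that knowledge to the 90-day intervention period, allocation is a code in an opaque envelope, and the arm shows itself when the code does or does not unlock the module. No section times the opening of the envelope or the entry of the code. A reader might infer that baseline is certainly recorded by people who know their arm; the documents support only that they may.
- **The nights probably precede treatment.** This stands in part. Return of the kit at the first treatment session suggests that recording is finished before supervised exercises begin. It is not airtight: the kit may be mailed instead, and an unlocked module already contains the recorded exercises. Within the 90 days only the OMTa arm has such a session.
- **Some sleep recording must already exist.** True: inclusion requires an OSA diagnosis with REI below 30. But that recording is not described as a study measurement and is not one of the two planned series, so it does not settle which nights give the baseline.
- **The planned treatment comparison is safe.** This stands for T2. A reader might infer that the primary result is biased. The documents do not support that: section 6.1 specifies no between-arm test of change, and nothing in them gives the size or direction of a shift.
- **Handling of missing baselines.** How a randomised participant without a usable baseline is analysed is open under either reading. It is a separate gap and is not counted here.

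**Conclusion.** Wrong as written; should be fixed. Confidence is high that the two sentences conflict and that no other section resolves them. Confidence is lower about the consequence, which rests on three assumptions: that the first series supplies baseline AHI, that the hand-out sentence would be followed, and that at least some participants learn their arm before or during the three nights. If all three hold, completion and recording quality of the baseline for change in AHI could differ by arm. No figure for that bias can be drawn from the documents. The point falls short of a critical flaw because the T2 comparison is unaffected, but a pre-randomisation recording that was never made cannot be recovered at analysis.

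**What to change.** Reconcile *Prior to the baseline consultation*, *Baseline evaluation*, *Randomization* and *Polysomnography (PSG)* so that all three baseline nights are recorded before allocation is revealed, and state that these nights supply baseline AHI. Either order of events achieves this.

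**(a) Record before the visit.** Issue the kit after signed consent, during the two-week diary period, and collect it at the baseline consultation. State when the kit for the second series is issued.

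*Cost:* an earlier hand-out or mailing, with consent secured first. The present text does not firmly place consent before the visit, since the same section allows exclusion to be assessed at the visit itself. Some kits go to candidates later excluded, for example under the diary rule: "Eligible candidates completing auto-monitoring less than 70% of the days prior to baseline assessment will be excluded". The documents give no exclusion rate. At an assumed 10% to 30%, reaching 100 randomised needs 100/0.9 = 111.1, so 112, to 100/0.7 = 142.9, so 143 candidates, which is 12 to 43 extra loans. Issuing kits late in the fortnight would avoid some of these.

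**(b) Keep the hand-out and delay allocation.** Issue the kit at the baseline consultation and open the randomisation envelope only after the three nights are recorded. This fits the present heading and scheduling text.

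*Cost:* a short delay and possibly one extra contact between the visit and allocation. The *Randomization* section would need rewording, including when the 90 days start and how participants get the e-mail address and password that share the envelope.

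Under either option, remove the first treatment session as the return point for the baseline kit, unless the text makes clear that allocation still follows the nights. The planned N is unchanged.

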#### *Outcome variables derived from polysomnography*

The desaturation severity parameter (Des Sev) was introduced by Kulkas et al in 2013. We have recently validated this variable with traditional variables such as the AHI, oxygen desaturation index, time below 90% saturation and nadir saturation, all assessing OSA severity.

Sleep efficiency (SE) will be calculated as the scored total sleep time divided by the total sleep period (TST). TST is defined as time from “lights out” to “lights on” divided by scored total sleep time. Sleep will be scored in accordance with the current version of the American Academy of Sleep Medicine (AASM) manual (version 2.6, 2020). The scoring will be done by expert sleep technologists at Reykjavik University Sleep Institute, using Noxturnal Research (version 6.1.0.30257). The following adjustments are needed for the SAS electroencephalography (EEG) signal:

- The low pass filter setting for the EEG will be changed from 0.3 Hz to 0.5 Hz.
- The peak to peak amplitude of the slow wave activity will be changed from 75  $\mu$ V to 50  $\mu$ V. Moreover, in the standard PSG, signals are measured over the frontal regions and referenced to the contralateral ear or mastoid (F4-M1, F3-M2). In the SAS it is referenced to the average of E4 and E3. The frontal filter available in the software will not be used.
- The frontal electromyography (EMG) does not show loss of tone in REM in the same manner as chin EMG. This means that REM rules that refer to chin tone are not useable for the most part. But it is however possible use the EMG frontalis to aid in scoring arousals (in rapid eye movement (REM) in particular). Arousals in REM will be scored if there is an abrupt change in the EEG to faster frequencies accompanied by an increase in EMG tone as in the AASM scoring rules.

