## **Participatory health technology**

The auto-monitoring application is named “Sleep Well”. The application communicates with a data cluster located in Iceland. The Sleep Well application contains a sleep diary. The diary is inspired by the consensus sleep diary developed by Carney and co-workers (appendix 1). Subjective, quantitative sleep data including sleep efficiency will be calculated based on the formulas proposed by Reed and co-workers. Exercises will be reported in an exercise diary in the sleep well application. A simple question for each of the three daily exercises will be delivered. Adherence to exercises will be assessed by the number of entries to the three daily questions. Administrative co-ordinators will support participants with technical issues.

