## **Outcomes**

The primary end point of the RCT is change in the AHI

Secondary endpoints:

1. Change in the Epworth Sleepiness scale and PROMs in the European Sleep Questionnaire.
2. OMTa adherence
3. Change in other conventional OSA severity indices (oxygen desaturation index, time below 90% saturation, nadir saturation) and change in novel OSA parameters in SAS identified in the development phase of the project.
4. Change in objective and subjective sleep quality (PSG and sleep diary, respectively).
5. Change in physiological parameters assessed by wearables.
6. Change in objective daytime functioning testing (PVT and Stroop test).
7. Change in self-reported self-efficacy as assessed by the PAM.
8. Changes in the Orofacial Myofunctional Evaluation with Scores (OMES).
9. Changes in the IOPI strength and endurance
10. Changes in hyoid position as assessed by a lateral cephalogram
11. Prediction of improvement in SDB severity by objective parameters from a 2D cephalogram obtained at baseline.

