# 10 Appendix

## 1 Paper version of sleep diary

### SOVNDAGBOK

Navn: \_\_\_\_\_ Spørsmål 1 til 4 fylles ut for sengetid, resten av skjemaet fylles ut om morgenen. Husk å notere dato.

Dato:	Eksempel 30.08.19	Mandag	Tirsdag	Onsdag	Torsdag	Fredag	Lørdag	Søndag
1. Hvordan har du fungert i løpet av dagen? 1 = veldig bra, 2 = bra, 3 = verken bra eller dårlig, 4 = dårlig, 5 = veldig dårlig	4							
2. Aktive mestringsstrategier for dårlig dagfunksjon :								
a. Antall minutter korte lurer/hvile med lukkede øyne	10 min							
b. Ca antall gjesp i løpet av våkentiden	10							
c. Minutter bevegelse for å aktivere våkenhetssystemet	2							
3. Har du tatt sovemedisin og/eller alkohol som hjelp til å sove ? Notér medikament, samt evt alkoholinntak	1 Imovane 1 glass rødvin							
4. Når gikk du til sengs? Når skrudde du av lyset?	22.30 23.00							
5. Hvor lang tid tror du det tok å sovne?	45 min							
6. Hvor mange ganger våknet du i løpet av natten?	3							
7. Hvor lang tid tror du at du totalt var våken i løpet av natten?	30 min							
8. Når våknet du opp om morgenen uten å få sove igjen? Notér tidspunktet for din endelige oppvåkning.	06.15							
9. Når stod du opp?	06.40							
10. Hvordan vurderer du nattens søvn? 1 = veldig lett, 2 = lett, 3 = middels, 4 = dyp, 5 = veldig dyp.	1							

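### The written formula for polysomnographic sleep efficiency gives sleep time squared over lights-out-to-lights-on time, in minutes, instead of a proportion

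*Combined protocol and SAP*

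**What the plan says.** The definition is in section 3.2, under Outcome variables derived from polysomnography, in two consecutive sentences. The first gives the ratio: "Sleep efficiency (SE) will be calculated as the scored total sleep time divided by the total sleep period (TST"). The second says what the denominator is: "TST is defined as time from “lights out” to “lights on” divided by scored total sleep time".

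The Outcomes section does not mention sleep efficiency by name. Its fourth secondary endpoint reads "Change in objective and subjective sleep quality (PSG and sleep diary, respectively"), and polysomnographic sleep efficiency reasonably belongs there. It is the only sleep-quality variable given a formula under the polysomnography heading.

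No other section supplies a formula for the polysomnographic measure. The section on participatory health technology mentions sleep efficiency, but only the subjective version from the diary, which follows a cited publication. Section 6, the statistical analysis plan, does not define it.

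**The concern.** A sleep efficiency is a proportion: time asleep over the time available for sleep. The first sentence has that structure. The second then makes the denominator itself a ratio, with scored sleep time beneath the interval. Putting one sentence into the other no longer gives a proportion. The abbreviation adds to the confusion: TST is attached to the total sleep period, whereas its letters fit total sleep time, which is the numerator. A programmer working from the text cannot tell which quantity TST denotes.

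If the rule were implemented as written, the variable would mix efficiency with sleep duration. A participant who simply spent longer in bed at the second recording, sleeping the same fraction of the time, would be counted as improved. A comparison of the arms on that variable would then not be a comparison of sleep efficiency.

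**Working it through.** **Inputs**

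- S = scored total sleep time in minutes (numerator, first sentence of the definition).
- B = time from lights out to lights on in minutes (second sentence).
- D = the denominator labelled TST; by the second sentence, D = B/S.

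The documents state no value of sleep efficiency, so there is no figure to reproduce. The check is a substitution followed by an illustration.

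**Substitution**

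SE as written = S/D = S/(B/S) = S²/B.

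Units: min²/min = min. D has no unit and is at least 1, because B is at least S.

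Writing E = S/B for the conventional ratio, SE as written = E × S. If S and B are both multiplied by k, E is unchanged and the written quantity is multiplied by k. It is therefore not a rescaled efficiency.

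**Illustration with the protocol's example night**

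Appendix 1, the paper sleep diary, has a filled-in sample column. Under the item "Når gikk du til sengs? Når skrudde du av lyset" the second entry, for lights off, is 23.00. The column also gives 45 min to fall asleep, 30 min awake during the night, final waking at 06.15 and rising at 06.40. These are diary estimates, not polysomnographic scores, and serve only as plausible values.

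- 23.00 to 06.15 = 435 min, so S = 435 − 45 − 30 = 360 min.
- Lights-on is not recorded. It is assumed to lie between 06.15 and 06.40, so B is between 435 and 460 min.

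| B (min) | D = B/S | Conventional S/B | As written, S²/B |
|---|---|---|---|
| 435 | 1.208 | 360/435 = 82.8% | 129,600/435 = 297.9 min |
| 460 | 1.278 | 360/460 = 78.3% | 129,600/460 = 281.7 min |

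**A longer night at the same efficiency**

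Lengthen the second row by 5%: S = 378, B = 483.

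- Conventional: 378/483 = 78.3%, unchanged.
- As written: 142,884/483 = 295.8 min, against 281.7 min, a rise of 5%.

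**Reversal of rank (assumed nights)**

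| S (min) | B (min) | Conventional | As written |
|---|---|---|---|
| 450 | 540 | 83.3% | 202,500/540 = 375.0 min |
| 380 | 420 | 90.5% | 144,400/420 = 343.8 min |

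The less efficient night receives the higher score.

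**The case against.** The best case for leaving this alone is that nobody would be misled. The two sentences contain every part of the correct formula: the first has sleep time over a period, the second names the period, and deleting the trailing clause and the misplaced abbreviation gives the usual ratio. Values near 300 could hardly pass for a proportion, and the recordings are scored by expert technologists. Sleep efficiency is not named among the eleven secondary endpoints; the primary endpoint is stated as "The primary end point of the RCT is change in the AHI", and section 6.2 does not use sleep efficiency. Nor has it been shown that the arms would differ in time in bed, so no direction or size of bias in the randomised comparison follows.

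Most of this is right, and it limits the weight of the point. It does not remove the error. The documents do not say who computes the variable, so detection is likely but not assured. More importantly, an analyst who notices the slip must depart from the written definition and choose a replacement, possibly with data in hand. The text does not fully settle that choice, because a total sleep period and the interval from lights out to lights on need not coincide. The title of the publication cited for the diary measure itself asks what the denominator should be.

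**Conclusion.** The definition is wrong as written. Followed exactly, it yields S²/B in minutes; on the example night that is 281.7 to 297.9, where a ratio of 78.3% to 82.8% is meant. The algebra needs no assumptions. The numerical illustrations rest on an assumed lights-on time and on assumed nights, and show only that the written quantity rises with night length and can reverse an ordering.

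The reach is limited: one unnamed component of one secondary endpoint, with no effect on the primary endpoint or the sample size, and no demonstrated bias between arms. It is almost certainly a drafting slip. It should still be corrected, because no other section gives a formula for this measure and a prespecified outcome should not depend on the analyst silently amending it.

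**What to change.** Replace the two sentences with a single definition: *SE (%) = 100 × TST / (time from lights out to lights on), where TST is the scored total sleep time.* Use TST for scored sleep time only, throughout. If the sponsor intended a different denominator, such as a sleep period with other start and end points, that interval should be defined explicitly before analysis begins.

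The cost is one corrected definition. Recording, scoring and data collection do not change.
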